## 5.4. Electrocardiogram (ECG)

ECG results and the change from baseline (heart rate, PR interval, RR interval, QRS interval, QTc interval) along with ECG interpretations will be summarized for each visit.

A subject data listing of ECG results will be generated.

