### **1.3. Endpoints**

#### **1.3.1. Primary Endpoints**

The primary endpoints of the study are adverse events (AEs), serious AEs (SAEs), electrocardiogram (ECGs), vital signs, and laboratory data (hematology, biochemistry, and urine data).

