## **3. GENERAL CONSIDERATIONS**

For continuous variables, mean, standard deviation, median, minimum, maximum, and number of subjects with non-missing data will be provided. For categorical variables, the number and percentage of subjects in each category will be provided.

Day 1 is defined as the first dose date. Study days after day 1 are calculated as: assessment date - first dose date + 1. Study days prior to day 1 are calculated as assessment date - first dose day.

Measurements collected from unscheduled visits, or repeated assessments will be included in the listings only, unless otherwise specified.

The descriptive summaries will be presented by total subjects for safety endpoints. Exploratory and efficacy endpoints will be presented in listings only. All summaries will be based on nominal visits.

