## 5. PRIMARY ANALYSES

All primary analysis will be based on the safety population. Descriptive summaries will be based on nominal visits.

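### Section 5.4 commits only to by-visit ECG summaries and a listing, so the specified tables do not fix how many subjects became abnormal after entry or, where a maximum is large, how many had a marked QTc rise

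*SAP*

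**What the plan says.** Section 1.3.1 names the primary endpoints as "adverse events (AEs), serious AEs (SAEs), electrocardiogram (ECGs), vital signs, and laboratory data". The ECG analysis is in section 5.4: heart rate and the PR, RR, QRS and QTc intervals, with change from baseline, "along with ECG interpretations will be summarized for each visit". The only other ECG output is a listing: "A subject data listing of ECG results will be generated".

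Section 3 says what a summary contains:
- Continuous: "For continuous variables, mean, standard deviation, median, minimum, maximum, and number of subjects with non-missing data will be provided".
- Categorical: "For categorical variables, the number and percentage of subjects in each category will be provided".

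Section 5 adds that "Descriptive summaries will be based on nominal visits", and section 3 that "Measurements collected from unscheduled visits, or repeated assessments will be included in the listings only, unless otherwise specified". Section 3.1 sets baseline at the last measurement up to and including the day of first dose in this study. Section 7 leaves table shells to a separate document. Neither section 5.4 nor any other section mentions an ECG shift table, a worst post-baseline ECG per subject, QTc categories or a QTc correction formula.

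**The concern.** In a single-arm, long-term study the useful ECG question is about subjects: how many developed an abnormality that they did not have at entry, and how many had a large QTc value or rise. By-visit summaries describe the group at each visit. A percentage abnormal at a visit mixes subjects who entered abnormal with those who became so. Percentages at successive visits cannot be added up, because the same subjects may be counted again. A mean QTc change hardly moves when a few subjects have large rises.

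The SAP treats adverse events differently. Section 5.1.1 counts subjects and tabulates them at their maximum CTCAE grade. ECG, also a primary endpoint, gets no per-subject worst-case summary, although a baseline is defined and Appendix 1 schedules ECGs at baseline and throughout treatment.

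**Working it through.** The plan gives no figure to reproduce: section 1.4 states that the sample size rests on no formal hypothesis. The check is therefore a reading of sections 3, 5 and 5.4 together, followed by arithmetic on what the resulting tables leave open.

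**Inputs from the SAP.** About 200 rollover and about 4 de novo subjects (section 1.1), so N is about 204. Rollover ECGs are at Screening/Baseline and every 6 months (Appendix 1, Table 2). Treatment-duration categories run to 30 months or more (section 4.6).

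**Assumed inputs.** The numbers abnormal, the SD of QTc change, and the 30 and 60 ms cut-offs. None is in the SAP.

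**1. Newly abnormal at one visit.** Suppose b subjects are abnormal at baseline and v at the visit, and all N have both ECGs. The two counts restrict the number newly abnormal only to the range max(0, v − b) to min(v, N − b).
- N = 200, b = 60, v = 60: max(0, 0) = 0 to min(60, 140) = 60.
- N = 204, b = 20, v = 20: 0 to min(20, 184) = 20.
- N = 204, b = 20, v = 30: 10 to min(30, 184) = 30.

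**2. Ever newly abnormal.** Even if 5 subjects were known to be newly abnormal at each of 5 visits, the number of different subjects could be anywhere from 5 (the same subjects each time) to 5 × 5 = 25.

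**3. Mean QTc change.** If k of 200 subjects rise by d ms and the rest do not change, the mean moves by k × d / 200.
- 5 × 60 / 200 = 1.5 ms.
- 3 × 70 / 200 = 1.05 ms.

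For scale, the standard error of the mean is 15/√200 = 1.06 ms to 20/√200 = 1.41 ms for an assumed SD of 15 to 20 ms.

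**4. Count of marked rises from mean and SD.** With mean change 0 and SD s, the one-sided Chebyshev (Cantelli) inequality limits the number with a rise of at least t to N × s²/(s² + t²). For N = 204 and t = 60 ms:
- s = 10: 204 × 100/3700, at most 5.
- s = 15: 204 × 225/3825, at most 12.
- s = 20: 204 × 400/4000, at most 20.
- s = 25: 204 × 625/4225, at most 30.

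A normal distribution would give about 0, 0.01, 0.3 and 1.7 subjects. The Cantelli figures are ceilings, not expectations, and use only the mean and SD. The planned median, minimum and maximum would narrow them.

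**5. What the maximum adds.** If no by-visit maximum change exceeds a cut-off, the scheduled-visit count above it is exactly zero. If one does, at least one subject exceeded it. How many did, and whether maxima at different visits belong to the same subject, stays open.

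**The case against.** The strongest reply is that section 5.4 contains no error: by-visit statistics with a listing are a valid, if minimal, plan for a descriptive study. Several parts of that reply have weight.

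- **The shells are not shown.** A reader might infer that no table in the study report will show new abnormalities. The SAP does not support that. Section 5.4 says only that results are summarized by visit; separate counts per category follow from the general rule in section 3, and a by-visit layout against baseline would be compatible with the text. What stands is that the SAP does not commit to one.
- **The maximum is reported.** A reader might infer that a marked QTc rise would be hidden. It would not: the maximum change at each scheduled visit reveals it. Only the number of subjects is left open, and only when a maximum is large. With no formal hypothesis, a comparison of the mean with its standard error decides nothing; it shows only that the mean is insensitive.
- **Other outputs exist.** The listing keeps every value, and an ECG finding reported as an AE enters the TEAE tables. But the first means counting by hand over about 200 subjects and repeated visits, and the second depends on the investigator reporting an AE.
- **Baseline follows earlier exposure.** About 200 of 204 subjects (98%) were previously treated with vatiquinone. A shift table would not show abnormality new since first exposure, and a reader might wrongly take it that way. It would still show change since entry, which is the change that section 3.1 defines.
- **QTc cut-offs have no source in the SAP.** That is correct; they must be offered as examples.

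**Conclusion.** The point holds in limited form. Read with sections 3 and 5, section 5.4 specifies tables that do not determine the number of subjects who became abnormal after entering this study. Where a by-visit maximum is large, they also do not determine the number with a marked QTc value or rise.

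The size depends on the data. With an assumed 60 of 200 abnormal at both times, the newly abnormal count is open from 0 to 60. With an assumed SD of 20 ms and mean change 0, the mean and SD alone allow up to 20 of 204 subjects with a rise of at least 60 ms. The rates, SDs and cut-offs are assumptions. That by-visit counts do not in general fix the number newly abnormal does not depend on them.

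No planned analysis is invalid and no collected information is lost. This is a cheap improvement to the tabulation of a primary endpoint.

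**What to change.** Keep the by-visit tables and listing, and add to section 5.4:

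1. A shift table of ECG interpretation, baseline category by worst post-baseline category, with each subject counted once and the severity order of the categories stated.
2. The n (%) of subjects by maximum post-baseline QTc and by maximum increase from baseline, in prespecified categories and with one named correction formula for all ECGs. Possible categories are above 450, 480 and 500 ms, and increases above 30 and 60 ms. These are assumed reporting categories, not SAP values, and the sponsor may prespecify others.
3. A sentence that all post-baseline ECGs, including unscheduled and repeat ones, count toward the worst value, as an exception to the listings-only rule in section 3. Without it, worst value is undefined.
4. A footnote that for rollover subjects both tables show change since entry to this study, not since first vatiquinone exposure.

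The cost is SAP wording and programming time for two tables from data already collected. No new assessments are needed.

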## 5.5. Physical examinations

A by-subject data listing of physical examination will be generated.

## 6. EXPLORATORY ANALYSIS

### 6.1. Seizure Frequency

Number of seizures for motor and non-motor seizures are collected in the seizure log. Seizure frequency will be based on the number of seizures per 28 days, calculated as the number of seizures over the time interval, divided by the number of the days in the interval, and multiplied by 28. Only “valid days” will be used in the calculations of seizures frequency per 28 days. A “valid day” is defined as the day where seizure counts information is present.

### 6.2. Newcastle Pediatric Mitochondrial Disease Scale (NPMDS)

The NPMDS assessment that corresponds to the subject’s age at the time of informed consent will be used. According to the NPMDS manual, NPMDS Sections 1 to 3 will be assessed by the investigator or subinvestigator (by the same physician during the entire study period, whenever possible), and NPMDS Section 4 will be assessed by the subject’s guardian (by the same guardian during the entire study period, whenever possible) and the subject (if he or she is 7 years of age or older and is able to complete the assessment). The investigator or subinvestigator are to record the dates and results of assessments in the CRF.

Cognitive function in NPMDS Section 3 is not planned to be measured.

### 6.3. CarerQoL-7D and PedsQL

The health-related quality of life, as measured by the CarerQoL-7D and the PedsQL questionnaires, will be captured in the electronic diary or recorded on the appropriate page of the CRF.

## 7. MOCK TABLES, LISTINGS, AND GRAPHS

The tables, listings, and graphs shells for the study will be provided in a separate document.

**8. VERSION HISTORY**

This Statistical Analysis Plan (SAP) for study PTC743-CNS-005-LSEP is based on the protocol Version 3.0 dated 25Jan2023.

SAP Version	Approval Date	Change	Rationale
1.0	04APR2025	Not Applicable	Original version

## APPENDIX 1. SCHEDULE OF EVENTS

**Table 2:** Schedule of Assessments – Rollover Subjects

Study Period	Screening/Baseline a	Treatment		EOT Visit	ET (6 Weeks After D/C) b
Study Month	Day 1	Telephone Visits 3 Months (84±7 Days) After On-Site Visits	Every 6 Months (168±7 Days)		
Informed consent	X c				
Demographics	X				
Medical history	X				
Vital signs	X		X	X	X
Height	X				
Weight	X	X d	X	X	X
Physical examination	X		X	X	X
12-Lead ECG	X		X	X	X
Urine pregnancy test (WOCBP) l	X		X	X e	X
Hematology (CBC w/ differential)	X m		X m	X m	X m
Serum chemistry	X m		X m	X m	X m
Coagulation panel	X m		X m	X m	X m
Urinalysis f	X		X	X	X
NPMDS g	X		X	X	X
CarerQoL-7D g	X h		X	X	X
PedsQL g	X h		X	X	X
Drug dispensed i	X	X	X		
Pre-/post-shipment contact j		X			
Drug compliance k			X	X	X
AE/SAE assessment	X	X d	X	X	X
Prior/concomitant medication	X	X d	X	X	X

**Abbreviations:** AE, adverse event; CBC, complete blood count; D/C, discontinuation; ECG, electrocardiogram; EOT, End-of-Treatment; ET, Early Termination; NPMDS, Newcastle Pediatric Mitochondrial Disease Scale; PedsQL, Pediatric Quality of Life Inventory™; SAE, serious adverse event; Study MIT-E, Study PTC743-MIT-001-EP; WOCBP, women of childbearing potential

a On-site visit applicable to all subjects rolling over to this study. For subjects rolling over from Study MIT-E, the Screening/Baseline Visit in this study will also be the Week 72 visit in Study MIT-E.

b Subjects who discontinue vatiquinone prematurely should complete an ET Visit.

c Informed consent will be signed before any study procedures. In case the subject/caregivers cannot attend the Screening/Baseline Visit in the clinic, remote consenting can be obtained.

d Clinical site staff will contact subject or parent(s)/legal guardian(s) every 3 months (by telephone if there is no clinic visit) to assess AEs, weight, and concomitant medications.

**PTC743-CNS-005-LSEP**  
**Statistical Analysis Plan**

---

- c At-home urine pregnancy test kits will be provided; subjects will be required to perform the test at home 30 days after the last dose of study drug and self-report the results via telephone.
- f Urinalysis by dipstick collection or serum test.
- g To be performed only for subjects previously enrolled in Study MIT-E.
- h These assessments will be performed at Week 72 of Study MIT-E and will be used as the Baseline assessment for this study.
- i Drug will be dispensed to the subject every 3 months.
- j Clinical site staff will contact the subject or parent(s)/legal guardian(s) to confirm details and timing of the upcoming study drug shipment. Post-shipment contact will confirm receipt of and condition of study drug.
- k Subjects or parent(s)/caregiver(s) or legal guardian(s) should return all used and unused bottles of vatiquinone as instructed in order to assess study drug compliance.
- l A pregnancy test will be administered every 6 months throughout the study. If urine pregnancy test is not possible, subjects can have a serum pregnancy test done.
- m Approximately 7.7 mL of blood will be drawn per visit

Note: If a site visit is not possible, a telephone visit and local laboratory may be performed and reviewed by the investigator to assess safety and concomitant medications.

**Table 3:** Schedule of Assessments – De Novo Subjects (France)

Study Period	Screening/ Run-In a	Baseline	Treatment				ET (6 Weeks After D/C) c
	Day -42 to Day -1		Day 0 ( $\pm 7$ Days)	Month 1 ( $28 \pm 7$ Days)	Month 3 ( $56 \pm 7$ Days)	Month 6 ( $84 \pm 7$ Days)	
Informed consent	X d						
Demographics	X						
Medical history	X						
Vital signs	X	X	X	X	X	X	X
Height	X	X					
Weight	X	X	X	X	X	X	X
Physical examination	X	X	X	X	X	X	X
12-lead ECG	X	X	X	X	X	X	X
Electroencephalogram (EEG)	X						X
Urine pregnancy test (WOCBP) i	X	X	X	X	X	X	X
Hematology (CBC w/differential)	X h	X h	X h	X h	X h	X h	X h
Serum chemistry	X h	X h	X h	X h	X h	X h	X h
Coagulation panel	X h	X h	X h	X h	X h	X h	X h
Urinalysis e	X	X	X	X	X	X	X
NPMDS		X			X	X	X
CarerQoL-7D		X			X	X	X
PedsQL		X			X	X	X
Drug dispensed f		X		X	X	X	
Drug compliance g				X	X	X	X
AE/SAE assessment	X	X	X	X	X	X	X
Prior/Concomitant medication	X	X	X	X	X	X	X

**Abbreviations:** AE, adverse event; CBC, complete blood count; D/C, discontinuation; ECG, electrocardiogram; EOT, End-of-Treatment; ET, Early Termination; NPMDS, Newcastle Pediatric Mitochondrial Disease Scale; PedsQL, Pediatric Quality of Life InventoryTM; SAE, serious adverse event; WOCBP, women of childbearing potential

a Screening will be conducted and completed in a maximum of 42 days (up to 14 days Screening and 28 days Run-in Period) prior to the Baseline Visit. Before the Run-in Period subjects will be trained in diary completion. The Run-in phase and initiation of the seizure diary completed during this phase of the study, will contain a minimum of 28 consecutive days of seizure data collected prior to the Baseline Visit. Ideally the subject will be instructed to start entering diary information the day after screening, so that the requisite number of days can be collected prior to the Baseline Visit. Laboratory tests from within 30 days of Screening are acceptable for entry to the study.

b After the Month 12 visits, subjects will return for on-site visits every 6 months and will have telephone visits every 3 months after the on-site visits, following the Schedule of Assessments for rollover subjects (Table 2).

c Subjects who discontinue vatiquinone prematurely should complete an Early Termination Visit.

d Informed consent will be signed before any study procedures. In case the subject/caregivers/legal guardian cannot attend Screening Visit in the clinic, remote consenting can be obtained.

e Urinalysis by dipstick collection.

- f Drug will be dispensed to the subject every 3 months. For Month 9, the clinical site staff will contact the subject or parent(s)/legal guardian(s) to confirm details and timing of the upcoming study drug shipment. Post-shipment contact will confirm receipt of and condition of study drug.
- g Subjects or parent(s)/caregiver(s) or legal guardian(s) should return all used and unused bottles of vatiquinone as instructed in order to assess study drug compliance.
- h Approximately 7.7 mL of blood will be drawn per visit.
- i In the event of pregnancy and, if the subject objects to their parents or guardians being informed, consultation without the presence of parents or guardians should be conducted.

**Table 4:** Schedule of Assessments – De Novo Subjects (Italy)

Study Period	Screening/ Run-In a	Baseline	Treatment				ET (6 Weeks After D/C) c
	Day -42 to Day -1		Day 0 ( $\pm 7$ Days)	Month 1 ( $28 \pm 7$ Days)	Month 3 ( $56 \pm 7$ Days)	Month 6 ( $84 \pm 7$ Days)	
Informed consent	X d						
Demographics	X						
Medical history	X						
Vital signs	X	X	X	X	X	X	X
Height	X	X					
Weight	X	X	X	X	X	X	X
Physical examination	X	X	X	X	X	X	X
12-lead ECG	X	X	X	X	X	X	X
Electroencephalogram (EEG)	X						X
Urine pregnancy test (WOCBP)	X	X	X	X	X	X	X
Hematology (CBC w/differential)	X h	X h	X h	X h	X h	X h	X h
Serum chemistry	X h	X h	X h	X h	X h	X h	X h
Coagulation panel	X h	X h	X h	X h	X h	X h	X h
Urinalysis e	X	X	X	X	X	X	X
Glutathione		X	X	X	X	X	X
NPMDS		X			X	X	
CarerQoL-7D		X			X	X	
PEDsQL		X			X	X	
Drug dispensed f		X		X	X	X	
Drug compliance g				X	X	X	X
AE/SAE assessment	X	X	X	X	X	X	X
Prior/Concomitant medication	X	X	X	X	X	X	X

**Abbreviations:** AE, adverse event; CBC, complete blood count; D/C, discontinuation; ECG, electrocardiogram; EOT, End-of-Treatment; ET, Early Termination; NPMDS, Newcastle Pediatric Mitochondrial Disease Scale; PedsQL, Pediatric Quality of Life InventoryTM; SAE, serious adverse event; WOCBP, women of childbearing potential

a Screening will be conducted and completed in a maximum of 42 days (up to 14 days Screening and 28 days Run-in Period) prior to the Baseline Visit. Before the Run-in Period subjects will be trained in diary completion. The Run-in phase and initiation of the seizure diary completed during this phase of the study, will contain a minimum of 28 consecutive days of seizure data collected prior to the Baseline Visit. Ideally the subject will be instructed to start entering diary information the day after screening, so that the requisite number of days can be collected prior to the Baseline Visit. Laboratory tests from within 30 days of Screening are acceptable for entry to the study.

b After the Month 12 visits, subjects will return for on-site visits every 6 months and will have telephone visits every 3 months after the on-site visits, following the Schedule of Assessments for rollover subjects (Table 2).

c Subjects who discontinue vatiquinone prematurely should complete an Early Termination Visit.

d Informed consent will be signed before any study procedures. In case the subject/caregivers/legal guardian cannot attend Screening Visit in the clinic, remote consenting can be obtained.

e Urinalysis by dipstick collection or serum test.

f Drug will be dispensed to the subject every 3 months. For Month 9, the clinical site staff will contact the subject or parent(s)/legal guardian(s) to confirm details and timing of the upcoming study drug shipment. Post-shipment contact will confirm receipt of and condition of study drug.

g Subjects or parent(s)/caregiver(s) or legal guardian(s) should return all used and unused bottles of vatiquinone as instructed in order to assess study drug compliance.

h Approximately 7.7 mL of blood will be drawn per visit.
